Assessment of mandibular bone invasion with Magnetic Resonance Imaging (MRI) using SWEEP Imaging with Fourier Transformation (SWIFT)

Principal Investigator: [name] MS

Co Investigators: [name] MPH; [name], MS, [name]

Version Number: 2

July 27, 2015

[figure not shown]
LIST OF ABBREVIATIONS

AE	Adverse Event/Adverse Experience
CMRR	Center for Magnetic Resonance Research
CRF	Case Report Form
GCP	Good Clinical Practice
HIPAA	Health Insurance Portability and Accountability Act
IRB	Institutional Review Board
MRI	Magnetic Resonance Imaging
PI	Principal Investigator
SAE	Serious Adverse Event/Serious Adverse Experience

PROTOCOL SUMMARY

Title:	Assessment of mandibular bone invasion with Magnetic Resonance Imaging (MRI) using SWEEP Imaging with Fourier Transformation (SWIFT)
Précis:	MRI scanning in 3T and 4T MR magnet will be performed on up to 20 patients with possible maxillofacial and/or mandibular bone invasion by applying newly developed sequences and clinically established MR sequences. We will then compare the conventional imaging results of the patients with 3T and 4T MRI results and post operative pathology results.
Objectives:	
The primary objective of this study is to improve the diagnostic accuracy and specificity of MRI in detecting the degree of bone involvement and invasion in oral cancer. The presence and degree of bone invasion determines the extent of surgery and has great effect on the morbidity of patients with oral cancer and bone/soft tissue tumors.
 
Primary: To demonstrate the efficacy of the MRI scanning in 3T and 4T MR magnet for patients with squamous cell carcinoma adjacent to, or involving, the mandible. Comparison will be made to histopathological sections as the “gold standard.”

Population:	We plan to enroll 20 subjects with a diagnosis of advanced squamous cell carcinoma of the oral cavity or osteoradionecrosis. All of those subjects enrolled will have findings concerning for mandibular invasion on physical examination or computed tomography imaging. Prior to surgery, patients will be consented for SWIFT imaging. Imaging will be conducted during a seven-day period prior to surgery.
Number of Sites:	University of Minnesota- CMRR
Study Duration:	Four years
Subject Participation Duration:	1 ½ hours for the study visit with MRI
Estimated Time to Complete	3 Years

Schematic of Study Design:

1 INTRODUCTION: BACKGROUND INFORMATION AND SCIENTIFIC RATIONALE

1.1 Background Information and Study Rational

The primary objective of this study is to improve the diagnostic accuracy and specificity of MRI in detecting the degree of bone involvement. The presence and degree of bone invasion determines the extent of surgery and has great effect on the morbidity of patients with oral cancer and bone/soft tissue tumors. The most important factor in the management is to accurately identify the presence of neoplastic invasion.

Unfortunately, detecting bone invasion and extension of bone involvement prior to surgery is often difficult with the currently available imaging techniques. MRI with high contrast resolution and the ability to perform multiplanar imaging plays an integral role in the delineation of tumoral involvement of the bone. Although MRI is an excellent tool in the assessment of bone invasion in carcinoma, its overestimation of cortical invasion and tumor extent to the bone marrow have been a diagnostic challenge, leading to false positive results. Like many of the musculoskeletal system tissues, cortical bone produces no signal with conventional MRI techniques, limiting the characterization of image contrast and differentiation of adjacent soft tissues.

A novel MRI technique called Sweep Imaging with Fourier Transformation (SWIFT) appears to be a suitable tool to overcome this challenge. The main advantage of SWIFT is to obtain signal from the cortical bone. We believe that the SWIFT technique will overcome the false positive results.

1.2 Potential Risks and Benefits

This study has the following risks:

1.2.1 Potential Risks

Screening Questionnaire

The questionnaire asks questions that are private in nature. Also, some people can be embarrassed by the questions. There is a risk that the information from the questionnaire could inadvertently be disclosed.

Magnetic Resonance Imaging (MRI)

MRI is routinely used in healthcare to look at tissues in the body. MRI scanners, the machines that take these images, have a strong magnetic field and have been cleared by the Food and Drug Administration (FDA) for routine use for patients. While there are no known health risks associated with these strong magnetic fields, some people report dizziness, mild nausea, headache, a metallic taste in the mouth, or sensations of flashing lights. These effects have been associated with movement of the head in a strong magnetic field. These symptoms, if present, disappear shortly after leaving the magnet. There are some risks linked with the MRI scanning procedure itself, which include:

1. Projectile Objects. Objects with magnetic properties, such as metallic objects, can be pulled into the magnet. These objects can be dangerous if they are brought into the magnet room. By keeping magnetic objects away from the magnet and by controlling access to the magnetic field area, we have minimized the chance of this occurring.
2. Claustrophobia. Some people may experience claustrophobia (fear of confined spaces), while inside the scanner. Once inside it is possible to stop the scanning and be removed at any time. Patients will be given a squeezable device, a bulb, which serves as an “emergency” button. The squeeze bulb will let MRI staff know immediately if the patient is experiencing claustrophobia, and they will terminate the scan. The MRI operators will be able to talk during the entire scanning process by two-way earphones and microphone communication system. Patients can also press a button inside the scanner to get their attention.
3. Energy waves. Another risk is presented by the energy waves used in the scanner. The power of the energy waves is well below the strength needed to heat the tissue in your body and cause harm, but any metal in contact with patient skin could heat up. This is why patients will be asked to remove all jewelry.

It is also possible that the scanner will cause peripheral nerve stimulation (stimulation of the nerves or muscles). If patients feel any tingling or unusual

sensations during the scan, or muscle contractions, they can use the squeeze bulb to alert the researcher immediately.

4. Loud Sounds. The MRI scanner makes loud banging noises during operation. Patients will be given earplugs to reduce the noise level. The noise generated by the operation of the scanner during a study is loud enough to cause hearing damage if patients do not wear hearing protection, which we will provide. If, even with the hearing protection we give patients, patients may find the noise from the scanner to be uncomfortable or painful, and can ask the scanner operator to stop the experiment immediately.

5. In addition, there is a risk of unknown effects related to participation in T4 tesla level MRI research. Long-term effects of exposure to high magnetic fields are unknown. Short term most people experience no ill effects from the strong magnetic field, but some people report dizziness, mild nausea, headache, a metallic taste in their mouth, or sensations of flashing lights.

6. The risks of exposure to high magnetic fields are unknown for fetuses. Therefore, if the participant is a female who is capable of becoming pregnant, and has any reason to believe that they might be pregnant, they should not participate in this study. The effects of taking MRIs on an unborn baby have not yet been proven to be safe or unsafe. If they think they may be pregnant, they must inform the investigator. The investigators strongly recommend that participants do not participate in this study if the participant thinks that they may be pregnant. Participants are ultimately responsible for their own decision to participate or not to participate in this study.

Potential Benefits

There are no direct benefits to participation. However, if anything abnormal is found and is considered to be a significant finding it will be reported to the patient's surgeon prior to surgery.

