2 OBJECTIVES

2.1 Study Objectives

To demonstrate the efficacy of the MRI scanning in 3T and 4T MR magnet for patients with mandibular bone invasion. Comparison will be made to histopathological sections as the “gold standard.”

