2.2 Study Outcome Measures

To determine how well the MR images will predict the presence of mandibular invasion, we will compare our results with clinical, operative, radiological and pathological findings (gold standard). Thus, patients will be asked to give permission to the investigators to access the relevant medical records.

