4 STUDY ENROLLMENT AND WITHDRAWAL

Patients 18 and older with oral cancer or osteoradionecrosis will be recruited for the study prior to their surgery. Subjects will be identified by their physician while seeking care for oral cancer or osteoradionecrosis in the Otolaryngology/Head and Neck Surgery clinic. Eligible patients will be recruited and consented in the Otolaryngology/Head and Neck Surgery clinic during their scheduled appointment. Consent will take place in the privacy of an exam room and consent will be obtained by a member of the research team that is familiar with the study. This appointment will occur before the patient undergoes surgery for their oral cancer.

Patients will have the study explained to them, will be given a full explanation of the risks of the study and the measures that will be taken to minimize them. Only individuals involved with this study will be obtaining consent from patients. The research staff will explain that the study is optional and participation will not influence the participant's treatment or relationship with the doctor of the University.

At any time during the course of the study participants can withdraw their consent and terminate their participation.

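### A significant research-MRI finding can reach the surgeon before the operation that supplies the reference standard, and the plan records neither the prior surgical assessment nor the disclosure

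*Combined protocol and SAP*

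**What the plan says.** The Protocol Summary places the research scan just before the operation ("Imaging will be conducted during a seven-day period prior to surgery") and compares it with conventional imaging and "post operative pathology results". Section 2.1 names the reference: "Comparison will be made to histopathological sections as the" gold standard. Section 2.2 lists more: "we will compare our results with clinical, operative, radiological and pathological findings (gold standard".

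Section 1.2, under Potential Benefits, adds that "if anything abnormal is found and is considered to be a significant finding it will be reported to the patient's surgeon prior to surgery". The sentence is not confined to incidental findings and makes no exception for bone invasion. Section 1.1 states: "The presence and degree of bone invasion determines the extent of surgery". Section 4 has staff explain that the study is optional and that "participation will not influence the participant's treatment or relationship with the doctor of the University".

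No section, and no row of Appendix A, asks for a dated MRI read, a record of the surgeon's view before a result is released, a log of what was reported, or an analysis that takes disclosure into account.

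**The concern.** A diagnostic accuracy comparison needs a reference standard that does not depend on the result of the test being assessed. Here the plan leaves a route by which it can. Patients are scanned because invasion is suspected, so unexpected or more extensive invasion on the research MRI fits the wording of the disclosure sentence. If the surgeon then takes more bone, or looks harder at one site, the specimen and the operative description are partly a product of the MRI. The route is one-sided, because an MRI that shows nothing generates no report.

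Two things are at stake. Agreement between MRI and pathology, and more directly between MRI and operative findings, may look better than it is. And without a record of who was told what, and whether the plan changed, nobody could later identify the affected patients. In a study of 20, a few would matter.

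**Working it through.** **Step 1: the chain in the text.**

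| Link | Where | What it establishes |
|---|---|---|
| Scan precedes surgery | Protocol Summary, Population | Up to seven days in which a result can be passed on |
| Result may be passed on | 1.2, Potential Benefits | Conditional on being abnormal and significant; the target condition is not excepted |
| Finding bears on the operation | 1.1 | Invasion sets the extent of surgery |
| Operation supplies the comparison | Protocol Summary, 2.1, 2.2 | Pathology, and in 2.2 also operative findings |

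Each link is stated. That a disclosure will actually alter a resection is a possibility left open, not a documented event.

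**Step 2: is there a figure to reproduce?** No. The only number is the 20 patients, given without a target sensitivity, specificity, prevalence or precision. The values below are assumptions that show direction and scale: true sensitivity (Se) and specificity (Sp) 0.80, prevalence 0.30 to 0.70. Disclosed MRI-positive patients are fully verified. In MRI-negative patients the corresponding probability is v. The calculation treats every MRI-positive patient as disclosed and puts the whole gap down to disclosure, so it leans towards a large effect.

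**Step 3: sensitivity.** Apparent Se = Se / (Se + (1 − Se) × v).

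- v = 1.0: 0.80 / 1.00 = 0.80, no bias
- v = 0.9: 0.80 / 0.98 = 0.82
- v = 0.75: 0.80 / 0.95 = 0.84
- v = 0.7: 0.80 / 0.94 = 0.85
- v = 0.5: 0.80 / 0.90 = 0.89

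With Se = 0.70 instead, v = 0.9 gives 0.70 / 0.97 = 0.72 and v = 0.5 gives 0.70 / 0.85 = 0.82. The shift is upward whenever v is below 1.

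**Step 4: specificity under two ways of handling bone that was not sectioned.**

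*Left out of the analysis.* Here v is the chance that bone at the suspect site reaches histology. Apparent Sp = Sp × v / (Sp × v + (1 − Sp)).

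- v = 0.7: 0.56 / 0.76 = 0.74
- v = 0.5: 0.40 / 0.60 = 0.67

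*Counted as free of invasion.* Here v is the chance that existing invasion is found. Missed invasion in MRI-negative patients joins the true negatives, so with prevalence p the numerator is (1 − p) × Sp + p × (1 − Se) × (1 − v), and the denominator adds (1 − p) × (1 − Sp). At v = 0.5:

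- p = 0.30: (0.56 + 0.03) / (0.59 + 0.14) = 0.81
- p = 0.50: (0.40 + 0.05) / (0.45 + 0.10) = 0.82
- p = 0.70: (0.24 + 0.07) / (0.31 + 0.06) = 0.84

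So specificity falls under one handling and rises slightly under the other. The documents do not say which applies.

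**Step 5: would leaving disclosed patients out solve it?** No. At 50% prevalence and 0.80/0.80, the expected number of MRI positives is 20 × (0.5 × 0.80 + 0.5 × 0.20) = 10. If all were disclosed and removed, only MRI-negative patients would remain, and apparent sensitivity would be 0 and specificity 1 by construction. With partial disclosure the distortion is smaller but of the same kind.

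**Step 6: scale against chance.** If 10 of the 20 had invasion and 8 were detected, the exact 95% interval would be 0.44 to 0.97. A shift of 0.02 to 0.09 in sensitivity sits well inside that interval, so the data could not reveal it. It has to be traced through records.

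**The case against.** The strongest reply is that feedback is conditional and its sentence may be meant as a significant-findings clause, not as a channel for the index result. All patients already have clinical or CT findings that raise the question of invasion, and those findings drive the resection. No section sends the MRI result to the pathologist. If conventional work-up already fixes the resection, v is close to 1 and the bias close to nil. This stands as a limit on size. It does not close the route, because the sentence as worded covers the target condition and section 1.1 says current imaging often leaves its presence and extent uncertain.

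A reader might infer that disclosure lowers specificity, by 6 to 13 points on the figures in step 4 (0.80 to 0.74 or 0.67). The documents do not support that: the sign depends on an unstated handling rule, and every input is assumed.

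A reader might also infer a flat contradiction between section 1.2 and section 4. The section 4 sentence opens by saying that the study is optional, and section 9.3 gives a similar assurance about declining, so it may be a promise of voluntariness. The wording still needs reconciling, because as written it denies an influence that section 1.2 makes possible.

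Finally, the surgical plan without the research MRI is not necessarily lost. Patients are usually approached at least a week before surgery and investigators have access to the records. But nothing requires that plan to be written down and dated. Whether MRI changes surgery is not a stated objective either, so the point rests on protecting the accuracy comparison.

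**Conclusion.** The concern holds in a limited form. The plan allows a positive research MRI, and not a negative one, to influence the operation and specimen against which it is assessed, and provides no record from which this could be traced. Apparent sensitivity can be inflated: by 0.02 to 0.09 from an assumed 0.80 when v runs from 0.9 to 0.5, and not at all when v is 1. The direction for specificity is undetermined, and the true size of either effect cannot be obtained from the documents. The conclusion rests on the disclosure sentence covering the target condition, which its wording allows, and on surgery responding to such a finding, which section 1.1 makes plausible but does not show. This is a cheap improvement to make before data accrue. It does not show that the comparison is invalid.

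**What to change.** Leave the disclosure decision as it is; whether and when to report is not a matter for this point. Change what is recorded and how it is reported.

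1. In section 5.3, record and date the research-MRI read before any result is released. Also record and date the surgeon's assessment of invasion and bone-resection plan, based on clinical findings and conventional imaging. The surgeon already verifies eligibility under section 5.2, so this part can be completed then and need not hold up any report.
2. Keep a log of each disclosure: date, content, and whether the plan changed.
3. In section 2.2, use the pre-disclosure assessment as the clinical comparator and keep histopathology as the reference standard in all patients. Report the pathology and operative comparisons for the full set and by disclosure or plan-change status. Do not exclude disclosed patients from the main comparison, since that selects on a positive MRI.
4. Reconcile the wording of section 1.2 (Potential Benefits) and section 4, so that participants are told the same thing in both.

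The cost is one short form, a log and one additional tabulation, with no extra scan, reader or procedure. The subgroups will be small in a study of 20, so the split by disclosure status is descriptive only.

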2 OBJECTIVES

2.1 Study Objectives

To demonstrate the efficacy of the MRI scanning in 3T and 4T MR magnet for patients with mandibular bone invasion. Comparison will be made to histopathological sections as the “gold standard.”

2.2 Study Outcome Measures

To determine how well the MR images will predict the presence of mandibular invasion, we will compare our results with clinical, operative, radiological and pathological findings (gold standard). Thus, patients will be asked to give permission to the investigators to access the relevant medical records.

3 STUDY DESIGN

This is a cross-sectional study to be conducted at the University of Minnesota. For this study we will enroll patients with possible maxillofacial and/or mandibular bone invasion. Patients 18 and older with oral cancer or osteoradionecrosis will be recruited for the study prior to their surgery. Subjects will be identified by their physician while seeking care for oral cancer or osteoradionecrosis in the Otolaryngology/Head and Neck Surgery clinic. Eligible patients will be recruited and consented in the Otolaryngology/Head and Neck Surgery clinic during their scheduled appointment. This appointment will occur before the patient undergoes surgery for their oral cancer or osteoradionecrosis. Patients that are deemed eligible, after reviewing their medical records, will complete the CMRR subject safety screening questionnaire.

All eligible and consented participants will have MRI scans obtained at the CMRR using the 3T and 4T magnet. Patients will also be asked to sign a HIPPA waiver allowing researchers to access their medical records including their clinical, operative, radiological and pathological findings.

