5 STUDY SCHEDULE

5.1 Screening/ Prior to Enrollment

- Review of medical records of any potentially eligible participants scheduled for a clinic visit. (Potentially eligible participants are also identified during tumor board.)
- Discuss the identified potential participant with PI to ensure eligibility prior to approaching participant about study.
- Introduce the study to the participant prior to their surgery. This usually needs to be done at least a week before surgery to ensure that the MRI can be scheduled.
- Review medical history to determine eligibility based on inclusion/exclusion criteria.

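### The protocol does not require the SWIFT reading to be recorded before the operative and pathology results are known, and it sets no masking of the reader.

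*Combined protocol and SAP*

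**What the plan says.** The study measures diagnostic accuracy. Section 2.1 names histopathology as the reference, and Section 2.2 states the comparison: "we will compare our results with clinical, operative, radiological and pathological findings (gold standard". Section 1.1 gives the hypothesis: conventional MRI overcalls cortical and marrow invasion, and SWIFT is expected to remove those false positives.

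On who may see what, Section 3 has patients sign a form "allowing researchers to access their medical records including their clinical, operative, radiological and pathological findings". Section 2.2 asks the same permission for the investigators. Neither sets a limit by role or by time.

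On what is known before the scan, the Protocol Summary says "All of those subjects enrolled will have findings concerning for mandibular invasion on physical examination or computed tomography imaging". Section 5.1 adds a screening step: "Discuss the identified potential participant with PI to ensure eligibility prior to approaching participant about study".

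On timing, the Protocol Summary says "Imaging will be conducted during a seven-day period prior to surgery". That fixes the scan, not its reading. The only text that implies a look at the images before the operation is under Potential Benefits in Section 1.2.1: "if anything abnormal is found and is considered to be a significant finding it will be reported to the patient's surgeon prior to surgery".

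Sections 5.3 and 6.1 describe acquiring the scan. Appendix A ends with the MRI being performed. None of them contains an image-reading step, a reader, a masking rule or a point at which a reading becomes final.

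**The concern.** Deciding whether tumour has crossed the cortex on an MR image involves judgement, and some calls will be equivocal. A reader who already knows the histology will tend to settle those calls in agreement with it. Fewer false positives and fewer false negatives are then recorded than the images alone would yield, so specificity and sensitivity both rise. The hypothesis is about false positives, so the equivocal calls in patients without invasion are the ones that decide it, and the error runs in the direction the study hopes to see. Once readings have been made with the answer known, no later analysis can restore independent ones.

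**Working it through.** The plan has no figure to reproduce: it states no effect size, target or comparator accuracy, prevalence of invasion, or sample-size calculation. The check has two parts.

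**1. Does the plan, followed exactly, prevent reading with pathology known?**

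- The scan precedes surgery (Protocol Summary), so a reading before pathology exists is possible.
- No reading is required at that time (Sections 5.3 and 6.1, Appendix A).
- The report to the surgeon (Section 1.2.1) is conditional on a significant abnormality. It is not a recorded call for every patient, and nothing stops a later re-reading.
- Access to operative and pathology findings has no time limit (Sections 2.2 and 3).

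Reading every scan after surgery with the pathology report open would therefore not be a deviation.

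**2. How much does one call weigh?**

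Input from the documents: N = 20 (Protocol Summary; also given as an upper limit). Assumptions: all 20 evaluable, one call per patient, and the values of n, s and f below.

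*Weight of one changed call = 1/n.*

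- Accuracy: 1/20 = 5 points. Fewer evaluable patients would make it larger.
- Specificity, by assumed number of histology-negative patients:

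| Negatives | One call moves specificity by |
|---|---|
| 5 | 20 points |
| 8 | 12.5 points |
| 10 | 10 points |
| 12 | 8.3 points |
| 15 | 6.7 points |

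*Expected inflation of specificity = f × (1 − s)*, where s is true specificity and f is the share of false positives revised to negative because pathology is known.

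| f | s = 0.5 | s = 0.6 | s = 0.7 |
|---|---|---|---|
| 0.10 | 5 points | 4 points | 3 points |
| 0.25 | 12.5 points | 10 points | 7.5 points |
| 0.50 | 25 points | 20 points | 15 points |

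These are averages; a single study can only move by whole patients. With 10 negatives and s = 0.6 there are 4 false positives. Revising one gives 7/10 = 70%, and revising two gives 8/10 = 80%.

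For scale, the exact 95% interval is 26% to 88% for 6/10 and 44% to 97% for 8/10. Those intervals describe sampling error only and would not reveal a shift caused by the reading conditions.

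The table covers knowledge of pathology only. Knowledge of CT or clinical findings pulls calls toward those findings, not toward histology. Since the Protocol Summary has every patient entering with a suspicious examination or CT, that knowledge could push borderline calls to positive and lower specificity. Where CT was reassuring and the examination was the reason for entry, it could do the opposite.

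**The case against.** Four points can be made in the plan's defence.

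- **The access sentence is a records authorization.** This is correct. Any accuracy study needs the reference results, and Section 2.2 shows that comparison is the purpose. A reader might infer that the plan directs image readers to see pathology, or that the PI who confirms eligibility also reads the scans. The documents say neither; they name no reader at all. What stands is an omission: the comparison needs access after the reading, and nothing puts the two in that order.
- **The scan and any report to the surgeon come before surgery.** True, and some images may well be looked at then. But this is not a fixed reading for each patient. It could also let SWIFT findings influence the operative findings that Section 2.2 uses for comparison.
- **The rule may sit elsewhere.** Section 10 mentions CRFs and Section 10.3 a Manual of Procedures, and neither is available here. If either already fixes the reading, a cross-reference would largely answer the point.
- **The bias cannot be sized.** A reader might infer from the table that it would be as large as the effect sought. The documents do not support that, because they state no effect. With s from 0.5 to 0.7, f would have to be 0.20 to 0.33 to match an assumed 10-point gain, and 0.40 to 0.67 to match an assumed 20-point gain. At f = 0.10 the inflation is only 3 to 5 points. Whether the bias falls below, equals or exceeds the effect depends wholly on these assumptions.

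**Conclusion.** The point holds as a gap in the index-test method. The protocol neither requires the SWIFT call to be recorded before operative and pathology results are available nor masks the reader. Readings made with pathology known would comply with it and could materially inflate sensitivity and specificity.

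The firm figure is the weight of one call on accuracy: 5 points with 20 evaluable patients. The 10-point weight on specificity rests on an assumed 10 histology-negative patients. The inflation figures are scenarios, not estimates.

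Knowledge of CT or clinical findings is also uncontrolled. It is a distinct weakness, and it should not be described as inflating specificity. The change is worth making because it is cheap now and the bias cannot be removed afterwards.

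**What to change.** Add to Sections 3 and 6.1:

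- For each SWIFT scan, the presence and extent of invasion are recorded on a CRF that is dated and locked before surgery.
- The reading is made from de-identified images, without CT, conventional MRI or clinical findings, where a team member who did not screen that patient is available.
- The locked reading is the one used in the accuracy analysis. Any later re-reading is reported separately.
- Pathology is reported without the SWIFT result.

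Add the locked reading as a row in Appendix A. The CRF should state what counts as a positive call, which the protocol does not define. The existing provision for reporting findings to the surgeon is left as it is.

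The lock before surgery does most of the work: at that point the operative and postoperative pathology results do not yet exist, so it protects against them even when no masked reader can be found. Masking deals with CT and clinical knowledge.

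Cost: protocol and CRF wording, de-identified image files, a short turnaround because scans fall within seven days of surgery, and a limit on which existing team member may read. As the protocol names no reader, the team should confirm who is available. Sample size, visits and scans are unchanged.
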